7.11.1.3 Sensitivity analysis

To evaluating the sensitivity and robustness of the primary analyses using the MITT population, the above analyses may be repeated in the ITT and PP Populations. Baseline factors, including demographics, disease characteristics, medical history, concomitant medication may be repeated for each analysis population. See Section 7.4 for further discussion on analyses populations.

7.11.1.4 Subgroup analysis

For the purpose of evaluating the sensitivity and robustness of the primary analyses, subgroup analyses including, but not limited to, the following subgroups may be performed:

- Age
- Gender
- Race

- Investigational sites
- COVID-19 standard of care treatments received:
 - o systemic steroids such as dexamethosone
 - o remdesivir

Baseline factors, including demographics, disease characteristics, medical history, concomitant medication may be repeated for each subgroup evaluated. If warranted, safety analysis may be repeated across subgroups.

7.11.2 Secondary Efficacy Evaluations

For secondary efficacy measures. the main timepoints of interest for analyses are baseline, Days 6, 14, 28, where data is available, unless otherwise specified.

7.11.2.1 Change in Ordinal Scale

Ordinal scale will be assessed at the Screening/Baseline, during the 5 days of treatment administration, and at any days where the patients are hospitalized through Day 28 and at Day 90. Baseline for the following analyses is defined as the last ordinal scale prior to administration of study drug. The number of patients with an improvement in the ordinal scale, defined as a change from baseline of ≥ 2 points, will be tabulated.

A MMRM model will be used to evaluate the change in ordinal scale, in which the change of ordinal scale from baseline on each timepoint of interest will be included as dependent variable and treatment, timepoint (categorical), and treatment-by-timepoint as fixed effects, patient as random effect, and the baseline value as a continuous covariate. An unstructured covariance matrix will be used for the MMRM analysis, unless the model does not converge, in which case the compound symmetry will be used.

Descriptive statistics for the overall treatment effect based on the MMRM model will include the least-squares (LS) mean difference, LS mean change from baseline for each treatment arm, their corresponding 95% CIs, and the p-values associated with the treatment difference compared to SOC. In addition, LS Means for the treatment differences at each timepoint of interest between treatment arms may also be provided with the same set of statistics derived from the same MMRM model defined above based on the MMRM estimates.

Additionally, the non-model based descriptive statistics for the corresponding change from baseline (overall) in the ordinal scale at each visit or timepoint of interest, change from baseline and maximum change from baseline will be evaluated and summarized by treatment arm. Except as noted in Section 7.1.1, unscheduled records will be excluded from the summaries at specific timepoints but will be included in the maximum change from baseline.

All available values of the ordinal scale, including change from baseline and maximum change from baseline will be listed by arm and patient. Refer to Appendix C of the Study Protocol for the ordinal scale categories.

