7.1 General Considerations

All safety analyses will be based on Safety Population; all efficacy analyses will be based on Modified Intent-to-Treat population, unless otherwise specified. Some specific sensitivity analyses of efficacy may be based on ITT and Per Protocol populations (for primary endpoints only). See Section 7.4 below for definitions of each analysis population.

All analyses will be considered as descriptive analyses. Derivation of two-sided 95% confidence intervals and p-values will be generated where applicable.

Time to event endpoints will be defined as the start date/time to the end date/time; censoring dates will be the last date/time the patient was determined to be event-free. Kaplan Meier methods will be used for time to event endpoint analyses; a log-rank test will be performed to compare the two survival curves. Timepoints estimates and median survival will be derived from the Kaplan Meier analysis. A Cox proportional hazards model may also be used to compare the two treatment arms using a hazard ratio.

Categorical endpoints will be calculated as the percentage of patients with the event, relative to the number of patients in a given analysis population (see Section 7.4). Stratified logistic regression approaches and/or repeated measures statistical approaches may be used to compare patients on the sargramostim and control arms, in addition to Fisher's Exact or Chi² tests (as appropriate). The randomization stratification factor for the baseline SOFA score (<6 versus \geq 6) will be considered for any stratified analysis.

Continuous endpoints will be summarized by n, means, medians, minimum, maximum, and 25th and 75th percentiles. Analysis of variance, analysis of covariance, and/or repeated measures statistical approaches may be used to compare patients on the sargramostim and control arms.

In the event that the underlying assumptions and/or distributions for a given statistical method are not satisfied, alternative statistical methods will be employed.

Additional exploratory analyses may be performed to evaluate the robustness and sensitivity of the study results, including but not limited to, additional evaluation of endpoints on other

analysis populations, subgroup analyses, treatment interactions, adjusted or stratified analyses, and/or alternative statistical methods.

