7.1.5 Missing Data Handling

In general, no imputation of missing data is planned for the primary analyses. However, for purposes of any sensitivity analyses, missing data may be imputed using last-observation-carried forward, or other advanced statistical imputation methods.

For the efficacy analyses based on oxygenation parameters, up to Day 6, if the assessment on Day 6 is not available, then the last prior non-missing value, after baseline will be used. See Sections 7.1.2, 7.1.3, and 7.1.4 for algorithm on determining assessments to be used for analysis.

Imputation for P(A-a)O₂ gradient, intubation rate and ordinal scale will not be performed.

If using last observation carried forward, a missing follow-up visit value will be imputed as that patient's previously observed value.

In the absence of any other specifications, the following rule will be used for missing time-toevent data:

• Patients who are alive (not lost to follow up) and did not experience the event of interest will be censored at the date last known to be alive and to be event-free.

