7.4 Analysis Population

The following analysis populations will be used to summarize the results from this study.

- Safety Population includes all patients who received at least one dose of sargramostim and/or SOC based on actual treatment received. Patients who did not receive any study treatment (either sargramostim and/or SOC) will be excluded from Safety Population. All safety analyses will be based on the Safety Population.
- Intent-to-treat Population (ITT) includes all patients who were randomized, and analyzed per the treatment arm as randomized. Selected efficacy analysis (P(A-a)O₂ and intubation rate) may also be performed based on ITT population for the purpose of sensitivity, unless otherwise specified.
- Modified Intent-to-treat Population (MITT): a subset of the ITT population that received at least one dose of any study treatment (either sargramostim and/or SOC). Efficacy analyses will be based on the MITT Population.
- **Per Protocol Population (PP)** includes all patients who were randomized and received at least one dose of sargramostim and/or standard of care based on the treatment assigned

at randomization and meet the eligibility criteria of this study. Selected efficacy analyses may also be performed based on the Per Protocol Population, unless otherwise specified.

- If the ITT, and PP populations are identical, or less than 10% different compared to the MITT population, then the selected efficacy analyses may not be repeated across the ITT and PP analysis population.
- Enrolled Population includes all patients who were eligible and signed informed consent form (ICF).

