7.11 Efficacy Evaluations

The primary and secondary efficacy endpoints of the study (as defined above in Sections 5.2.1 and 5.2.2 above) will be analyzed as specified below. If the primary and secondary efficacy endpoints show meaningful results, then the exploratory efficacy endpoints (Section 5.2.3 above) will be summarized.

Key timepoints of interest for endpoints include Days 1-6, Day 14, and Day 28, where data are assessed and/or available, unless otherwise specified. All available efficacy data will be tabulated and presented for all patients in the Modified Intent-to-Treat (MITT) Population; see Section 7.4.

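### As the SAP reads, patients discharged or dead by Day 14 or Day 28 get no ordinal score, so the MMRM treats known outcomes as missing at random

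*SAP*

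**What the plan says.** SAP 7.11.2.1 has the ordinal scale assessed at screening or baseline, on the five treatment days, and then "at any days where the patients are hospitalized through Day 28 and at Day 90". The MMRM takes change from baseline at each timepoint of interest, with unstructured covariance. From it, "Descriptive statistics for the overall treatment effect based on the MMRM model will include the least-squares (LS) mean difference", with confidence intervals and p-values. By-visit summaries are also planned.

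Two sections list the timepoints. Section 7.11.2 says "the main timepoints of interest for analyses are baseline, Days 6, 14, 28, where data is available"; section 7.11 says "Key timepoints of interest for endpoints include Days 1-6, Day 14, and Day 28". Day 90 is in neither list, so the Day 90 score does not help at Days 14 and 28.

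On missing values, 7.1.5 says that imputation for the P(A-a)O₂ gradient, "intubation rate and ordinal scale will not be performed".

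Section 7.11.2.1 also tabulates "The number of patients with an improvement in the ordinal scale", meaning a change of at least 2 points, without naming a day. The denominator is fixed elsewhere: 7.1 expresses categorical endpoints "relative to the number of patients in a given analysis population", and 7.4 says "Efficacy analyses will be based on the MITT Population".

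The SAP uses both of the facts needed to score these patients: survival status in 7.11.2.2 and discharge date in 7.11.2.5. Section 7.11.2.5 even offers an optional rule for in-hospital deaths when computing length of stay. Section 7.11.2.1 has no counterpart. The scale levels are left to protocol Appendix C.

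**The concern.** Read together, these sections leave a patient who is home or dead at Day 14 or Day 28 without a score on that day. A likelihood-based MMRM is valid if scores are missing at random. It would in effect predict the absent score from patients who are still scored. Here the score is absent because the patient has left hospital or died, which are plausibly the best and worst outcomes on such a scale, and both are known. The by-visit summaries would describe only those still in hospital.

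Treatment can change who is discharged and who dies, so the arms would be compared on groups selected after randomization. At stake is the first-listed secondary endpoint. Its result could understate a recovery benefit, or point a different way from the mortality analysis, with nothing in the plan to warn the reader. For the improvement count, discharged patients are likely improvers, yet the SAP does not say whether a discharged patient without a score counts as improved.

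**Working it through.** The SAP gives no figure to reproduce: 7.2 states that the sample size rests on no statistical assumptions. The check is of direction only. Scale levels and daily rates below are assumptions; Days 6, 14, 28 and the 80:40 split come from the SAP.

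**Method.** Simulate large arms, then fit the same model (treatment by day, baseline, unstructured covariance, maximum likelihood) in two ways: with discharge and death scored at their own levels, and with inpatient scores only.

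**Model A.** Eight levels, higher worse: 1–2 discharged, 3–7 inpatient, 8 death. There are 40,000 patients per arm.
- Daily discharge rate: 0.12 at level 3, half that at level 4, none at higher levels or before Day 6.
- Daily death rate: 0.04 or 0.05 at levels 6–7, one twentieth of that below.
- Treated arm: discharge 0.20 (faster discharge); death 0.02 instead of 0.05 (fewer deaths); or discharge 0.20, death 0.03 and faster improvement (all three).

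Treatment difference at Days 6/14/28; negative favours treatment; the mean is the sum divided by 3:

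| Scenario | Discharge and death scored | Mean | Inpatient scores only | Mean |
|---|---|---|---|---|
| No effect | +0.02/+0.02/+0.03 | +0.02 | +0.01/+0.03/0.00 | +0.01 |
| Faster discharge | −0.05/−0.22/−0.26 | −0.18 | +0.02/+0.12/+0.23 | +0.12 |
| Fewer deaths | −0.10/−0.24/−0.45 | −0.26 | +0.03/+0.07/+0.12 | +0.07 |
| All three | −0.32/−0.80/−1.06 | −0.73 | −0.12/−0.10/+0.01 | −0.07 |

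In these scenarios only 18–37% of an arm is still in hospital at Day 28: about 10–12 of 40 controls and 15–30 of 80 treated patients.

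**Model B.** Six levels, higher better: 1 death, 2–5 inpatient, 6 discharged. There are 90,000 patients, with log-normal frailty of SD 0.4.
- Daily step up: 0.05/0.12/0.15 from levels 2/3/4; discharge 0.30 from level 5.
- Daily step down: 0.05/0.04/0.02 from levels 3/4/5.
- Daily death: 0.045/0.008/0.002/0.001 from levels 2–5.

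Overall difference; positive favours treatment:

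| Scenario | Completed scores | Inpatient scores only | All living patients scored, deaths not |
|---|---|---|---|
| No effect | −0.01 | −0.01 | – |
| Recovery rates × 1.5 | +0.42 | +0.08 | +0.36 |
| Death rates × 2 | −0.13 | +0.13 | +0.09 |
| Death rates halved | +0.09 | −0.06 | −0.05 |

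Both models agree on direction. With no effect, none is created. A recovery benefit shrinks (and reverses in Model A). A death-only effect changes sign.

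**Against the trial's precision.** SE = SD × √(1/80 + 1/40) = SD × 0.194.
- Model B scale, assumed SD 1.0 to 1.5: SE 0.19 to 0.29. The death-only differences are then at most 0.13/0.19 = 0.7 SE.
- Model A, fewer deaths, Day 28: the shares in hospital/discharged/dead are 0.26/0.46/0.29 (control) and 0.37/0.49/0.14 (treated). Placing these groups at levels 5, 1.5 and 8 gives SDs of about 2.8 and 2.4, so SE ≈ √(2.8²/40 + 2.4²/80) = 0.52. The difference of 0.45 is 0.45/0.52 = 0.9 SE.
- Varying Model B's rates, frailty and end-level scores at random moved the completed-score difference to between +0.01 and +0.23 with fewer deaths, and between −0.02 and −0.43 with more. On the same SEs, 0.23 is 0.8 to 1.2 SE. Only the extreme harm settings go clearly beyond that (0.43 is 1.5 to 2.3 SE).

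**The case against.** The strongest reply is that the sentence in 7.11.2.1 describes data collection, and the schedule and scale sit in the protocol, which is not at hand. Sections 7.1.1 and 7.5 name Day 14 and Day 28 as visits or key timepoints. Sections 7.11.3.4 and 7.12.4 list Day 28 apart from the inpatient days or the day of discharge. Survivors may therefore be scored then. If Appendix C has a death level and the CRF records it, death too is a recorded score, and the bar on imputation is not engaged. This stands as a condition on the finding. It does not remove it, because how discharge and death enter the MMRM is an analysis rule and the SAP states none. A level recorded on the day of death or discharge is also not a Day 14 or Day 28 score unless a rule carries it there, and a programmer could read 7.1.5 as forbidding that.

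The Up to Day 6 fallback in 7.1.4 may or may not cover this scale, but it cannot help at Days 14 and 28. Last observation carried forward, allowed generally for sensitivity analyses in 7.1.5, would carry an inpatient level past discharge or death.

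It is also fair to say that the simulations rest on invented rates and scales. Tallying sign reversals over random rate sets would look firmer than it is, because the smallest differences (+0.01, −0.02) are no larger than the Monte Carlo error of 0.01–0.02. A reader might also infer that the improvement count must favour the wrong arm. That needs a Day 14 count with unscored patients taken as not improved, and the SAP states neither. Counted at any time, the difference kept its sign in the same simulations.

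**Conclusion.** The point holds conditionally and should be repaired. As 7.11.2.1 and 7.1.5 read, known discharge and death become missing values in the MMRM and drop out of the by-visit summaries, unless the protocol schedule or Appendix C supplies scores. Under assumed rates, this tends to shrink a recovery benefit, and a difference in deaths alone can take the wrong sign. If survivors do have scores, most of the recovery benefit returns (+0.36 of +0.42 in Model B), but the death problem remains if deaths go unscored.

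No size is claimed. A reader might infer that the reported difference is certain to be biased, or that deaths are certain to go unscored; without the protocol, the SAP establishes neither. In the worked cases the death-only differences are under one standard error for 80:40 patients, so a reversal would seldom be discernible in this trial. The separate gap in the improvement count is plain from the text: no day, and no rule for discharged or dead patients.

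The stakes are limited. The endpoint is secondary, 7.1 and 7.2 make all analyses descriptive, and mortality has its own analysis in 7.11.2.2, so an ordinal result distorted by deaths would conflict with that analysis rather than hide it.

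**What to change.** In 7.11.2.1 and 7.1.5, state that at each post-treatment analysis timepoint an MITT patient who has died, or who was discharged alive and not readmitted, is assigned the matching Appendix C level from the survival and discharge dates. Say that this is observed status, not imputation. If Appendix C has no such level, or several levels for discharged patients, state the rule used instead.

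Run the MMRM and the by-visit summaries on these completed scores, and keep missing at random only for patients whose status is unknown. Name the day for the improvement count, taken over all MITT patients with deaths counted as not improved.

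The cost is a few sentences and one derivation from dates that 7.11.2.2 and 7.11.2.5 already use. There are two downsides to state in the plan. A discharged patient is assumed to stay at the discharged level unless readmission is recorded. The result also becomes a composite that includes death on the scale's numeric spacing, although the planned MMRM already treats that spacing as numeric.

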7.11.1 Primary Efficacy Evaluations

For primary efficacy measures based on oxygenation parameters, the main timepoints of interest for analyses are baseline, up to Day 6 for P(A-a)O₂ gradient, and by Day 14 for rate of intubation, where data are available, unless otherwise specified.

See Sections 7.1.2, 7.1.3, and 7.1.4 for algorithm on determining assessments to be used for analysis.

As ABG was required only at baseline and at Day 6/Post-Treatment visit (or day of discharge if earlier), the number of patients with complete data at all study visit days is expected to quite limited. Therefore, the primary timepoint for analyses for data based on ABG will be up to Day 6.

7.11.1.1 Oxygenation Up to Day 6

The $P(A-a)O_2$ gradient will be derived using arterial blood gas assessment via arterial puncture at baseline and up to Day 6, or day of discharge whichever is earlier. See Sections 7.1.2, 7.1.3, and 7.1.4 for algorithm on determining assessments to be used for analysis.

The change from baseline and percentage from baseline is defined as:

Percentage Change from Baseline= Change from Baseline/ Baseline

The P(A-a)O₂ gradient, the percent change from baseline up to Day 6 will be tabulated based on "unchanged or deteriorated" [no difference or positive percent change from baseline] and "improved" [negative percent changer from baseline] by 10% change increments. In addition,

the percentage of patients with $a \ge 33\%$ improvement for each treatment arm will be provided. For both of these analyses, a Chi-square, or Fisher's exact test (or stratified logistic model) will be generated to compare the treatment arms. Alternative cutoffs for defining meaningful improvement may be used (e.g., 25%, 50%), with similar analyses methods as above.

The maximum change from baseline and maximum percentage change from baseline will be summarized up to Day 6, and for the study duration.

Maximum percentage change from baseline is defined as:

Maximum Percentage Change from Baseline= Maximum Change from Baseline/ Baseline

For these analyses, the baseline is defined as the last available assessment prior to administration of study drug (see Section 7.1.2 above). Except as noted in Section 7.1.1, unscheduled records will be excluded from the summaries at specific timepoints but will be included in the maximum change from baseline.

A listing of all P(A-a)O₂ gradient measurements will be provided.

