A Mixed Model Repeated Measures (MMRM) model will be used to evaluate the change in $P(A-a)O_2$ gradient, in which the change of $P(A-a)O_2$ gradient from baseline on each study day up to Day 6 (or day of discharge) will be included as dependent variable and treatment, study day (categorical), and treatment-by-study-day as fixed effects, patient as random effect, and the baseline value as a continuous covariate. An unstructured covariance matrix will be used for the MMRM analysis, unless the model does not converge, in which case the compound symmetry will be used. The change in $P(A-a)O_2$ gradient up to Day 6 will be evaluated by this MMRM model.

Change in oxygenation/respiratory parameter of P(A-a)O₂ gradient will also be presented by waterfall plot.

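### Both MMRMs force one baseline slope across all timepoints; a baseline-by-time term is a cheap gain in precision, mainly for the Day 14 and Day 28 ordinal contrasts

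*SAP*

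**What the plan says.** SAP 7.11.2.1 sets the outcome: "the change of ordinal scale from baseline on each timepoint of interest will be included as dependent variable". The model terms are "treatment, timepoint (categorical), and treatment-by-timepoint as fixed effects, patient as random effect, and the baseline value as a continuous covariate". On covariance it says "An unstructured covariance matrix will be used for the MMRM analysis, unless the model does not converge", with compound symmetry as the fallback. The overall LS mean difference, its confidence interval and p-value are to be reported. The by-timepoint results are optional: "LS Means for the treatment differences at each timepoint of interest between treatment arms may also be provided".

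SAP 7.11.1.1 gives the P(A-a)O2 model the same structure: "treatment, study day (categorical), and treatment-by-study-day as fixed effects, patient as random effect, and the baseline value as a continuous covariate". It runs to Day 6 only.

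Neither list contains a baseline-by-time interaction.

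Two sections bear on which timepoints enter the ordinal model. SAP 7.11, on efficacy in general, says "Key timepoints of interest for endpoints include Days 1-6, Day 14, and Day 28". SAP 7.11.2, on secondary endpoints, says "the main timepoints of interest for analyses are baseline, Days 6, 14, 28". Section 7.11.2.1 does not itself name the timepoints.

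**The concern.** The outcome is change from baseline. Soon after baseline a patient's score is still close to the baseline score, so change has a regression slope on baseline near 0. As the weeks pass the link weakens and the slope moves towards -1. A model with one slope cannot follow this. Under an unstructured covariance the shared slope is a weighted average that leans heavily on the earliest timepoints, so the late contrasts are adjusted with a slope that belongs to early follow-up.

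Two things are at stake at Days 14 and 28. The standard error is larger than the collected data allow. And if the arms differ at baseline by chance, which is plausible with 80 and 40 patients, part of that difference stays in the estimate.

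**Working it through.** The SAP states no precision figure, SD or correlation, and SAP 7.2 says the sample size rests on no statistical assumption. There is therefore no figure of the plan's own to reproduce, and every size below is conditional on stated assumptions.

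**Inputs from the SAP:** arms of 80 and 40 (6.1, 7.2); the model terms, outcome and covariance above; timepoints either Days 6, 14, 28 (7.11.2) or Days 1-6, 14, 28 (7.11).

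**Assumed:** complete data; SD 1 at every time, including baseline; correlation between two times equal to ρ^(days apart), with ρ = 0.95 or 0.97. The baseline-to-Day-28 correlation is then 0.24 or 0.43.

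**Formulas.** Let s be the vector of true slopes of change on baseline, S the residual covariance given baseline, and σ²_B the baseline variance.
- Common slope: b = (1'S⁻¹s)/(1'S⁻¹1).
- Variance of the Day 28 contrast: (1/80 + 1/40) × [S₂₈ + (s₂₈ − b)² σ²_B].
- With a separate slope per timepoint the second term is zero, so the inflation is 1 + (s₂₈ − b)² σ²_B / S₂₈.

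**Worked case: Days 6, 14, 28, ρ = 0.95.**
- s = 0.95^t − 1 = −0.265, −0.512, −0.762.
- The weights in b are 0.653, 0.100, 0.247, so b = −0.413.
- S₂₈ = 1 − 0.95^56 = 0.943.
- The slope gap at Day 28 is −0.762 + 0.413 = −0.35, and 0.35² = 0.122. Inflation is 1 + 0.122/0.943 = 1.13.
- Overall LS mean difference: the mean slope is −0.513, so the gap is −0.10. The residual variance of the three-timepoint mean is 0.424. Inflation is 1 + 0.010/0.424 = 1.02.

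**Same case with Days 1-6, 14, 28.** Day 1 takes 0.894 of the weight and Day 28 takes 0.061. Then b = −0.109, the gap is −0.653, and inflation is 1 + 0.427/0.943 = 1.45.

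| Timepoints | ρ | Day 28 variance inflation | Overall LS mean inflation |
|---|---|---|---|
| 6, 14, 28 | 0.95 | 1.13 | 1.02 |
| 6, 14, 28 | 0.97 | 1.13 | 1.04 |
| 1-6, 14, 28 | 0.95 | 1.45 | 1.15 |
| 1-6, 14, 28 | 0.97 | 1.33 | 1.12 |

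**How the size depends on the assumptions.**
- With 5% measurement noise, Day 28 inflation is 1.10-1.11 for the three-timepoint set and 1.25-1.34 for the eight-timepoint set.
- If the spread widens gradually and the baseline SD is 0.35-0.5 of the Day 28 SD, inflation is only 1.00-1.07 for either set.
- If the slope does not change over time, inflation is 1.00.
- A different parameterisation sets residual SD 2.0 at Day 28, baseline SD 0.5-1.2 and 7-day residual autocorrelation 0.5-0.9. The Day 28 SE with separate slopes is then 0.387. With a common slope it is 0.395-0.434 for the eight-timepoint set (raw-score slope falling from 0.98 to 0.20) and 0.390-0.427 for the three-timepoint set (0.8 to 0.2). The most extreme three-timepoint case is (0.427/0.387)² = 1.22, above the 1.13 in the table.

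**Bias and imbalance.** In 4,000 simulated trials per scenario the mean error was within about two Monte Carlo standard errors of zero. A one-SE chance baseline imbalance is √(1/80 + 1/40) × σ_B = 0.194 σ_B. With σ_B of 0.5-1.2 and a slope gap of 0.3-0.85, it leaves 0.03-0.20 scale points in the Day 28 estimate.

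**P(A-a)O2 at Day 6.** SAP 7.11.1 notes: "As ABG was required only at baseline and at Day 6/Post-Treatment visit (or day of discharge if earlier"). Assume raw-value slopes falling from 0.9 to 0.4 over Days 1-6. If 0-20% of patients also have ABGs on Days 1-5, the variance is 0-7% above that of the separate-slope model.

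**The case against.** The strongest reply is that little follows from this. SAP 7.11 applies its timepoints unless otherwise specified, and 7.11.2 does specify Days 6, 14 and 28 for secondary endpoints. On that reading the larger figures fall away. The required output is the overall difference, where the loss is at most about 4%, and the by-timepoint differences are optional. All patients enter with acute hypoxemia, so baseline scores may well be narrower than Day 28 scores, which shrinks the loss further. The analyses are descriptive (7.1, 7.2). Section 7.1 also allows other methods if assumptions fail. Nearly all of this stands and sets the severity. The 7.1 clause helps least: it names no check of slope constancy and no replacement model, and a choice made later, in an open-label trial, is weaker than fixing the term now.

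Three stronger readings are tempting, and the documents support none of them.
- **Less precise than no baseline adjustment.** Against raw Day 28 scores this happens under some assumptions only. Against unadjusted change, which is the SAP's own outcome, the equal-SD cases above give 0.70-0.95 times the variance. The other parameterisation gives 0.88-1.02 when slopes fall, and up to 1.15 only if they rise.
- **A biased treatment estimate.** Randomisation keeps it unbiased on average.
- **A stated loss of power.** The trial has no powered hypothesis, so any such figure would need an invented effect size.

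**Conclusion.** The point holds as a low-severity, inexpensive improvement. Both models fix a single baseline slope next to treatment effects that vary by time. If the true slope changes over 28 days, the late ordinal contrasts lose some precision and some protection against chance imbalance.

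On the more natural reading (Days 6, 14, 28), I would put the excess variance at about 0-13% at Day 28 and 0-4% for the overall difference. One more extreme assumption set reaches 22% at Day 28. On the wider reading (Days 1-6, 14, 28) the Day 28 excess is about 0-45%, and the top of that range needs a spread as large at baseline as at Day 28. All of this assumes complete data and a baseline correlation that decays with time.

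For P(A-a)O2 the effect is small because ABGs were required only at baseline and Day 6. The ordinal model carries the point.

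**What to change.** In SAP 7.11.2.1 add the baseline-by-timepoint interaction to the fixed effects, so that the overall and by-timepoint LS mean differences come from a model with a separate baseline slope at each timepoint. Name the timepoints that enter the model in the same sentence, since the size of the problem depends on them.

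In 7.11.1.1 add baseline-by-study-day for consistency, limited to days with enough ABG data to estimate a slope. The gain there is small.

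The cost is one line in each section. The ordinal model gains 2 fixed-effect parameters with Days 6, 14, 28, or 7 with Days 1-6, 14, 28. The P(A-a)O2 model gains up to 5 with Days 1-6. This is in a trial of about 120 patients. The downside is that slopes on sparse days will be poorly estimated. If the slope is in fact constant, almost nothing is lost.
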